## 9.2 Endpoints

### 9.2.1 Primary Endpoints (including definitions)

Time to resolution of cholestasis (direct bilirubin < 2 mg/dL without subsequent rebound above 2 mg/dL).

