### 4.0 SELECTION AND ENROLLMENT OF SUBJECTS

#### 4.1 Inclusion Criteria

Infants on parenteral nutrition who have congenital or acquired gastrointestinal diseases that place them at risk of short bowel syndrome (SBS) or prolonged parenteral-nutrition-dependence, will be considered eligible for the study if either (1) they remain cholestatic (bilirubin > 2 mg/dL) after 4wks of reduced lipids and trace elements, or (2) If their direct bilirubin is > 6 mg/dL in the absence of suspected or proven infection.

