#### 4.3 Study Enrollment Procedures

Clinical nutrition rounds, between the PI and the NICU dietician, occur every 1-2wk as part of the routine clinical care of the infants. As part of the clinical care of the infants, and infant identified as having cholestasis or PNALD (direct bilirubin  $\geq$ 2 mg/dL on two consecutive occasions  $\geq$ 8d apart) have their intralipid infusion rate reduced to 1 g/kg/d and have the trace elements added to their parenteral nutrition reduced. The current protocol will not alter this.

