### 5.0 STUDY TREATMENT (*OR INTERVENTION*)

#### 5.1 Regimens (*or Intervention*), Administration, and Duration

The intervention is the use of omegaven (an intravenous fish oil emulsion) in place of intralipid (the currently used soybean oil intravenous lipid emulsion, until parenteral nutrition is discontinued, or until cholestasis resolves.

Parents of eligible patients will be approached for consent for their infants to take part in the study. If they agree, the PI will contact the FDA to receive an IND number for the infant (copies of the required FDA paperwork will be sent to the IRB). Omegaven will be ordered from the manufacturer. Once the IND number is received, the IRB will be informed of the subjects IND number. Once the IND number is received, and communicated with the IRB, and the omegaven is received, intralipid infusions will be

Version date 1/12/2018

stopped and omegaven will be infused at the rate of 1 g/kg/d. Clinically-indicated labs will be monitored, as for all patients on prolonged parenteral nutrition, i.e. CBC, electrolytes, BUN, Creatinine, ALT, AST, Alkaline phosphatase, albumin, total bilirubin, direct bilirubin and serum triglycerides will be measured at least every 2 weeks. No additional labs will be required as part of the study.

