### 5.3 Pharmacy: Product Supply, Distribution, and Accountability

#### 5.3.1 Study Product Acquisition

Parents of eligible patients will be approached for consent for their infants to take part in the study. If they agree, the PI will contact the FDA to receive an IND number for the infant (copies of the required FDA paperwork will be sent to the IRB). Omegaven will be ordered from the manufacturer. Once the IND number is received, the IRB will be

Version date 1/12/2018

informed of the subjects IND number. Once the IND number is received, and communicated with the IRB, and the omegaven is received, intralipid infusions will be stopped and omegaven will be infused at the rate of 1 g/kg/d.

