### 6.2.2 Entry Evaluations

Clinical nutrition rounds, between the PI and the NICU dietician, occur every 1-2wk as part of the routine clinical care of the infants. As part of the clinical care of the infants, and infant identified as having cholestasis or PNALD (direct bilirubin  $\geq 2$  mg/dL on two consecutive occasions  $\geq 8$ d apart) have their intralipid infusion rate reduced to 1 g/kg/d and have the trace elements added to their parenteral nutrition reduced. The current protocol will not alter this. If they remain cholestatic (bilirubin  $> 2$  mg/dL) after 4wks of reduced lipids and trace elements, or (2) if their direct bilirubin is  $> 6$  mg/dL in the absence of suspected or proven infection they will be considered eligible for the study.

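### Does the unstated time zero in 9.2.1, with no bilirubin threshold required at first infusion, let falls before omegaven count as resolution?

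*Combined protocol and SAP*

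**What the plan says.** Section 9.2.1 gives the sole endpoint as "Time to resolution of cholestasis (direct bilirubin < 2 mg/dL without subsequent rebound above 2 mg/dL"). It names no origin for the time. Section 9.1 says only that descriptive summaries will be produced, with time to resolution as the example. The Analyses section (the second one numbered 9.5) refers back to what precedes it.

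Omegaven does not start at eligibility. Sections 5.1 and 5.3.1 put consent first, then the request for an individual IND number and the product order. After the IRB has been told, "and the omegaven is received, intralipid infusions will be stopped and omegaven will be infused". No duration is given for these steps and no bilirubin check is attached to the start. Section 5.1 says that "total bilirubin, direct bilirubin and serum triglycerides will be measured at least every 2 weeks", and it asks for no extra tests.

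On entry, criterion (1) in 4.1 applies if "they remain cholestatic (bilirubin > 2 mg/dL) after 4wks of reduced lipids and trace elements". Criterion (2) reads "If their direct bilirubin is > 6 mg/dL in the absence of suspected or proven infection". Section 6.2.2 repeats criterion (1), again without naming the fraction. The routine-care definition in 4.3 does name it: "infant identified as having cholestasis or PNALD (direct bilirubin" at or above 2 mg/dL on two consecutive occasions at least 8 days apart.

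**The concern.** A time-to-event endpoint needs an origin, and here at least four are possible: eligibility, consent, receipt of the IND number and first infusion. They differ by a wait whose length the documents do not give. Under 4.3, Intralipid and trace elements are already reduced before entry, so direct bilirubin might fall in the wait without any omegaven. Read literally, an infant who falls below 2 mg/dL before the first infusion and never rebounds meets 9.2.1 with a time at or near zero.

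Hypothesis 1.1 is about timing: resolution related in time to omegaven. A fall that comes first cannot support it, and this is the only endpoint of an uncontrolled cohort. The missing word in criterion (1) adds to the worry. Total bilirubin is measured too, so a literal reader could admit an infant with total above 2 mg/dL and direct below it, who would be resolved on arrival.

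**Working it through.** There is no stated sample-size or power figure to reproduce: 9.4 gives a cap of 25 and 9.1 disclaims testing. The check has three parts.

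**1. What the text implies about origin and baseline**

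- Hypothesis 1.1 concerns infants who have cholestasis, and 5.1 gives omegaven until cholestasis resolves. Both presuppose that cholestasis is present when treatment starts.
- The stopping rule (5.1, 6.2.4, 8.1) ends omegaven once direct bilirubin has been below 2 mg/dL for more than 2 weeks. An infant below 2 mg/dL that long before the start would already meet it.
- Infants are reviewed every 1-2 weeks (4.3), and the team may withhold omegaven for any reason (5.1).
- In 6.2.2 the direct-bilirubin definition of cholestasis stands just before criterion (1) in the same paragraph. Remaining cholestatic can only sensibly mean remaining so by that definition.

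None of these is a scoring rule. Together they point to first infusion as time zero and direct bilirubin as the measure.

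**2. How many infants could be affected**

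The fall needed to reach 2 mg/dL from a value b is 1 − 2/b:

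| Direct bilirubin (mg/dL) | Fall needed |
|---|---|
| 2.5 | 20% |
| 3 | 33% |
| 6 | 67% |

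Criterion (2) infants, above 6 mg/dL, need a fall of more than two thirds. The route is therefore mainly open to criterion (1) infants, who qualify only because 4 weeks of reduced lipid and trace elements did not clear their cholestasis.

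The one related rate is in 2.1: 2/46 = 4.3% of soybean-oil historical controls resolved while on parenteral nutrition. Applied to 25 infants, 25 × 2/46 = 1.1. The wait would usually cover only part of such a follow-up (an assumption, since its length is not stated), so one infant is near a rough ceiling. Those controls received 1-4 g/kg/d, not reduced lipid, so the figure is a guide only.

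**3. Effect on the summary**

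Assume that k of 25 infants are already below 2 mg/dL at first infusion and counted as resolved, and that the rest resolve at the cited 19/42 = 45.2%. The apparent share is (k + (25 − k) × 19/42)/25.

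| k | Apparent share resolved |
|---|---|
| 0 | 45.2% |
| 1 | (1 + 24 × 0.4524)/25 = 47.4% |
| 2 | (2 + 23 × 0.4524)/25 = 49.6% |

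The exact 95% interval for 11/25 is 24.4% to 65.1%. A shift of about 2 percentage points per infant is small beside that. The 45.2% is resolution while still on parenteral nutrition, a limit that 9.2.1 does not impose, so these shares are illustrative.

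The direction depends on the origin. Timed from first infusion, a fall before treatment makes the summary look better. Timed from eligibility or consent, the wait adds untreated time to every infant and lengthens the times. The net direction is therefore not fixed.

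**The case for a change.** The strongest case for acting is that this is the only endpoint of an uncontrolled cohort and the hypothesis is about timing. The data stay in the medical record (11.1) and data management is marked not applicable (11.2), so the origin could be settled after outcomes are known. A descriptive time summary still needs an origin, even if no infant falls early, and writing one down would cost a few sentences and no new tests.

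The omission is real, and the safeguards in the clinical text are not scoring rules. But no plausible reading other than first infusion serves the hypothesis, and the routine direct bilirubin values are in the record for an analyst to see and report.

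A written baseline rule would also not close the gap. With tests only required every 2 weeks, an infant at 2.3 mg/dL on day −13 who is below 2 mg/dL by day −1 without a further test would still pass as cholestatic at baseline. No scoring sentence can detect that fall from the existing tests.

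**Conclusion.** No change to the plan follows. Section 9.2.1 leaves the origin and the baseline condition unwritten, but this is a gap that an analyst would fill sensibly: time from first infusion, show the last routine direct bilirubin before it with its date, and identify any infant already below 2 mg/dL. The missing word in criterion (1) is a clerical slip, and the surrounding text makes the intended fraction clear. It is inconsistent with 4.3 and 9.2.1, but it does not create a separate entry population.

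The likely effect is at most about one infant in 25, or roughly 2 percentage points on an assumed 45.2% resolved share, well inside sampling error. This rests on three assumptions: that the historical 4% is a fair rough ceiling, that the wait is short relative to that follow-up, and that the cited 45% is a usable benchmark. The documents cannot confirm any of them. If several infants did fall below 2 mg/dL before starting, the routine values would largely show it. The exception is a fall after the last pre-infusion test. The study describes a compassionate-use cohort and tests nothing, so no error rate or decision depends on this point.

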### 9.2.2 Secondary Endpoints (including definitions)

None

### 9.2.3 Substudy Endpoints (as required)

None

## 9.3 Randomization and Stratification

N/A

## 9.4 Sample Size and Accrual

Up to 25 subjects recruited

*(For main study and substudies.)*

## 9.5 Monitoring

As above

## 9.5 Analyses

As above

## 10.0 PHARMACOLOGY PLAN

N/A

## 11.0 DATA COLLECTION AND MONITORING AND ADVERSE EVENT REPORTING

### 11.1 Records to Be Kept

The patient's participation will be documented in the EMR. All labs will be measured for clinical reasons, not for reasons related to the study. They will stay in the EMR. A list of patients on the study will be kept in a secure filing cabinet by the PI.

### 11.2 Role of Data Management

N/A.

Version date 1/12/2018

### 11.3 Clinical Site Monitoring and Record Availability

N/A

### 11.4 Expedited Adverse Event Reporting to

An external Data Safety Monitor ([name], Professor of Pediatrics, Section of Neonatology, Department of Pediatrics, Baylor College of Medicine and Texas Children's Hospital, Houston, TX) will be informed of all subjects recruited to the protocol. He will be informed, by e-mail, of any laboratory results on the subjects at least monthly, or within 7d of any significant change in biochemical data. He will have the authority to withdraw a subject from the protocol at any time. He will be unaware of the subject name, but will be made aware of any pertinent clinical data relevant to lab interpretation (e.g. presence or absence of infection, underlying GI diagnosis, amount of enteral feeds etc). Subjects will be identified by an anonymous number when communicating with the external safety monitor.

The IRB will also be informed of any adverse events. The FDA will be informed of any adverse events only to the extent required by law.

## 12.0 HUMAN SUBJECTS

### 12.1 Institutional Review Board (IRB) Review and Informed Consent

This protocol and the informed consent document (pending) and any subsequent modifications will be reviewed and approved by the IRB or ethics committee responsible for oversight of the study. A signed consent form will be obtained from the subject (or parent, legal guardian, or person with power of attorney for subjects who cannot consent for themselves, such as those below the legal age of consent). The consent form will describe the purpose of the study, the procedures to be followed, and the risks and benefits of participation. A copy of the consent form will be given to the subject, parent, or legal guardian, and this fact will be documented in the subject's record.

### 12.2 Subject Confidentiality

All laboratory specimens, evaluation forms, reports, and other records that leave the site will be identified by coded number only to maintain subject confidentiality. All records will be kept locked. All computer entry and networking programs will be done with coded numbers only. Clinical information will not be released without written permission of the subject, except as necessary for monitoring by IRB, the FDA, the , the OHRP, or the pharmaceutical supporter(s) or designee.

### 12.3 Study Discontinuation

The study may be discontinued at any time by the IRB, the pharmaceutical supporter(s), the FDA, the OHRP, or other government agencies as part of their duties to ensure that research subjects are protected.

Version date 1/12/2018

## 13.0 PUBLICATION OF RESEARCH FINDINGS

Publication of the results of this trial will be governed by policies.

Version date 1/12/2018

